## **Statistical Analysis Plan**

## **Primary Outcomes**

All caregivers-regardless of randomized study condition-complete questionnaires on three separate occasions during this study: baseline, 3-months, 6-months. The four outcome measures include changes over the 6-month study period for the following scales: Zarit Burden Interview-Short Form, a questionnaire measuring caregiver burden (Zarit, Reever, & Bach-Peterson, 1980). 12 items are rated on 0-4 scale. Range: 0-48. No subscales. Higher scores represent worse outcomes; Center for Epidemiological Studies Depression Scale (CES-D), a questionnaire measuring depression (Radloff, 1977). 20 items are rated on a 0-3 scale and summed (range = 0-60). There are no subscales. Higher scores represent worse outcomes. The clinical cut-off is usually set at a score of 16; Beck Anxiety Inventory (BAI), a questionnaire measuring anxiety (Beck, Epstein, Brown, & Steer, 1988). 20 items are rated on a 0-3 scale and summed (range= 0-60). Higher scores indicate worse outcomes. There are no subscales. A score greater than 36 is considered to be clinically significant.; and Satisfaction with Life Scale, a questionnaire measuring overall life satisfaction and well-being (Diener, Emmons, Larsen, & Griffin, 1985). 5 items scored on a 1-7 scale and summed (Range = 5-35). Lower scores indicate worse outcomes. A score of 20 is considered neutral with higher scores considered increasingly more satisfied and lower scores considered increasingly more dissatisfied.

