## **Statistical Methods**

Design: Caregivers will be randomized into two groups: Active In-Home Technology System and Limited In-Home Technology System. Subjects will be randomized 1:1. Randomization of participants in each group will be determined by People Power employees. Analyses of caregiver health and well-being will use 2 X 3 (Condition [active treatment vs control] X Time [time 1 vs time 2 vs time 3]) mixed model analysis of variance. In all analyses, significant main effects and interactions will be decomposed using a priori or post hoc comparisons depending on whether they are hypothesized or not. Bonferroni corrections will be used to control for Type I error resulting from multiple comparisons. Statistical Power. Tests of hypothesized Group differences (active treatment vs control condition) for caregiver health and well-being will have .80 power to detect a medium effect size (one-tailed, alpha = .05). Using repeated measures analysis of variance, tests of the interaction of Condition (2 groups) X Time (3 assessments) will have power of .99 to detect a medium effect size (correlation between repeated measures r = .5, alpha = .05).

Analysis: Descriptive statistics will be used to summarize all the clinical characteristics and demographic outcomes. These will be summarized overall, by treatment group, by assessment time, and by treatment group and time. Continuous variables will be summarized using means, standard deviations, and ranges. Categorical data will be summarized by number and percent. To evaluate the treatment effects, we will use repeated measures ANOVAs. The other predictors will be treatment group, and time (baseline, 3-months, and 6-months for caregiver outcomes). To evaluate treatment effects, an interaction term between treatment group and time will be included

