to examine treatment group-related differences in the assessments for each outcome. Each significant interaction will be followed up with paired t-tests to examine treatment differences at each set of time points. Although this study involves 4 outcomes, we do not plan formal multiple comparison adjustments if the results fit a coherent pattern that is consistent with the context of similar studies. In this case, each result will reinforce the other, rather than detracting from one another, as required by formal multiple comparisons adjustments such as Bonferroni. Conversely, if only one or a very few measures reach statistical significance and their directions and/or magnitudes do not coherently fit with our a prior expectations, then we will note that the result(s) with p < 0.05 lack plausibility and could be due to chance, despite meeting the conventional cutoff for statistical significance.

Missing Data: If subjects either cannot or refuse to complete surveys we will use a sensitivity analysis approach in dealing with these missing data by performing analysis with 2 versions of scores: 1) with missing item interpolated using mean replacement by group, and 2) only using responses with 0% missing data. If the results differ for the two approaches, then we will report on the differences.

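### Whether the four unranked primary outcomes are adjusted for multiplicity depends on an undefined coherence judgement made after results are seen, so family-wise error is bounded (at most .20) but not held at .05

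*SAP*

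**What the plan says.** **Outcomes.** SAP, Primary Outcomes, puts four scales (burden, depression, anxiety, life satisfaction) under one heading: "The four outcome measures include changes over the 6-month study period for the following scales". None is ranked above the others.

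**Confirmatory test.** SAP, Statistical Methods (Analysis), evaluates treatment effects through the interaction of treatment group with time, fitted for each outcome. The power statement in the same section says that "tests of the interaction of Condition (2 groups) X Time (3 assessments) will have power of .99 to detect a medium effect size", at alpha .05.

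**Adjustment across outcomes.** The Analysis paragraph then says "we do not plan formal multiple comparison adjustments if the results fit a coherent pattern that is consistent with the context of similar studies". The reason given is that in such a pattern "each result will reinforce the other". The opposite case arises "if only one or a very few measures reach statistical significance and their directions and/or magnitudes do not coherently fit with our a prior expectations". Its only consequence is a note that results below 0.05 lack plausibility and may be chance findings.

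**Bonferroni.** Earlier, under Design, the SAP says that "significant main effects and interactions will be decomposed using a priori or post hoc comparisons", and the next sentence says that "Bonferroni corrections will be used to control for Type I error resulting from multiple comparisons". It does not say which comparisons form the family.

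**The concern.** A multiplicity rule protects the error rate only if it is fixed before the results are known. Here the condition for not adjusting is a property of the results. The SAP does not say how many outcomes must be significant, in which direction, by how much, or which similar studies set the standard.

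The opposite case does not supply a threshold either. Its caution needs two things together: few significant results, and a misfit with expectations. One significant outcome out of four that agrees with expectations does not meet the second condition. Nor is it plainly a coherent pattern of mutually reinforcing results. This is a likely outcome of a four-outcome trial, and the SAP does not say how it would be judged.

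The stake is the meaning of a positive report. If one favourable scale at p < .05 is presented as success, a reader cannot tell from the SAP what false-positive rate stands behind it.

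**Working it through.** **Inputs from the documents.** Four outcomes with one interaction test each, and alpha .05 (SAP). 60 caregivers per arm, so N = 120 (Protocol, Randomization). Three assessments, repeated-measures correlation .5 and interaction power .99 for a medium effect (SAP, Statistical Power).

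**Assumptions.** The medium effect is taken as f = .25. The between-outcome correlation r is set at 0, .3, .5, .7 and .9. Neither is given in the documents.

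**1. The SAP's power figure.** With noncentral F on 2 and 2 × 118 = 236 degrees of freedom, lambda = f² × N × 3 / (1 − .5) = .0625 × 120 × 3 / .5 = 45, and power at .05 is above .999. Leaving out the correlation term gives lambda = .0625 × 120 × 3 = 22.5 and power .992. The stated .99 is met either way.

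**2. Bound on family-wise error.** Four tests at .05 give at most 4 × .05 = .20 under any dependence. If independent, 1 − .95⁴ = .185.

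**3. Error under different readings of a positive result, with no true effect.** The first and last rows are simulated for the 2-degree-of-freedom interaction tests. The middle three use four equicorrelated normal statistics, one contrast per outcome, with favourable and significant meaning z > 1.96. They approximate the reading and are not the SAP's F test.

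| Reading | r = 0 | .3 | .5 | .7 | .9 |
|---|---|---|---|---|---|
| Any of four interactions at .05 | .185 | .175 | .158 | .133 | .096 |
| At least one favourable and significant | .096 | .087 | .078 | .065 | .047 |
| All four favourable, at least one significant | .012 | .041 | .057 | .062 | .047 |
| At least two favourable and significant | .004 | .011 | .017 | .023 | .027 |
| Any of four interactions at .0125 | .049 | .047 | .044 | .038 | .027 |

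Check on row 2 at r = 0: 1 − .975⁴ = .096.

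The error rate runs from well under .05 to about .185 depending on which reading is used, and the SAP does not fix one. The last row shows what a threshold of .05 / 4 = .0125 gives.

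**4. Power cost of a fixed threshold.** Solving for exactly .99 power at .05 gives lambda = 21.67; power at .0125 is then .963. With lambda = 45, power at .0125 is still above .999; with lambda = 22.5 it is .970.

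**5. The Bonferroni sentence.** It directly follows the sentence on breaking down significant effects, so follow-up comparisons are its natural object. On that reading the four outcomes have no adjusted threshold. If it was meant to cover the four outcomes, it conflicts with the Analysis paragraph, which deals with those outcomes specifically and waives adjustment.

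**The case against.** **The waiver is narrower than it first looks.** It applies to a coherent pattern, and the SAP gives a reason for it. This stands in part: the two coherent readings in the table carry at most about .06. But the SAP never says that a positive claim requires such a pattern.

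**The isolated favourable result does not carry the full any-of-four rate.** A reader might infer that one favourable scale has a false-positive rate of up to .185. The documents do not support this. That figure counts non-directional tests, including results against treatment, and the SAP treats a few results that do not fit expectations as possible chance findings. For the favourable case the approximate range is .096 down to .047, so at very high correlation there is no excess.

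**Bonferroni might be the default when coherence fails.** The text does not exclude this, so it is too strong to say that the SAP plainly contradicts itself or certainly uses .05 throughout. But the opposite case names only a note, and the sentence's position points to follow-up comparisons. The ambiguity itself needs removing.

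**Group tests might double the family.** The power statement says "Tests of hypothesized Group differences (active treatment vs control condition) for caregiver health and well-being will have .80 power", one-tailed, and a reader might infer eight confirmatory tests. The documents give this little support. The Analysis paragraph ties treatment effects to the interaction, and nowhere is a Group main effect alone said to count as success. The size of this point therefore rests on four tests.

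**Conclusion.** The concern holds in bounded form. The rule for the four primary outcomes is undefined and depends on the results, no adjusted threshold for them is stated, and the Bonferroni sentence either does not reach them or conflicts with the waiver. Family-wise error is at most .20 but is not controlled at .05.

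Its size depends on the reading adopted. Any significant interaction gives about .185 to .096 and a favourable isolated result about .096 to .047, while strictly coherent patterns are near or below .05. These figures rest on the assumed correlations and, for the directional and coherent readings, on a one-contrast normal approximation.

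This should be fixed. It does not invalidate the design, and the evidence from a truly coherent favourable pattern would be little affected.

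**What to change.** Before results by arm are seen, delete the coherence condition as a basis for adjusting and state, for example:

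> For each of the four primary outcomes, the Condition × Time interaction is the confirmatory test. The four interaction tests will be judged by the Holm procedure at family-wise .05, whatever the pattern of results. Group main effects are supportive. The Bonferroni correction under Design applies to follow-up comparisons within each ANOVA.

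Coherence across the scales can stay as a matter for discussion. Naming one primary outcome in advance, with the interaction as its test, would also close the gap.

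**Cost.** This changes SAP wording only; no data collection or sample size changes. The smallest p-value must be below .05 / 4 = .0125; later Holm steps are less strict (.05 / 3 = .0167, then .025, then .05). A test with exactly the stated .99 power at .05 has about .963 at the first step. With N = 120, repeated-measures correlation .5 and assumed f = .25, power stays above .99.

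### The missing-data rule yields two results and makes neither decisive; its group-mean filling counts filled values as observed, which inflates the condition-by-time test if the mean is taken by arm and visit

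*SAP*

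**What the plan says.** The Missing Data paragraph closes the SAP's Statistical Methods section. Its trigger is: "If subjects either cannot or refuse to complete surveys we will use a sensitivity analysis approach". The analysis is then run on two sets of scores: "with missing item interpolated using mean replacement by group, and 2) only using responses with 0% missing data". For a conflict between them it says: "If the results differ for the two approaches, then we will report on the differences". Nothing ranks the two, and nothing allows for the uncertainty of the filled values.

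Three terms are left open. The trigger speaks of surveys, but the filling speaks of an item. *Group* may mean the arm, or the arm at a given visit. *Responses* may mean one visit's questionnaire, or all of a caregiver's questionnaires.

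Both sets feed the same test, a repeated measures ANOVA in which the treatment effect is the interaction of condition with time (baseline, 3 and 6 months). The SAP's Primary Outcomes section defines the outcomes as changes: "The four outcome measures include changes over the 6-month study period for the following scales". These are a 12-item burden scale, two 20-item scales (depression and anxiety) and a 5-item life-satisfaction scale. Neither document gives an expected missing rate.

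**The concern.** There are two faults. First, a sensitivity analysis needs a main analysis to test, and none is named. If the two results conflict, the reader is told so but not what is concluded. Second, filling with a mean makes the ANOVA count caregivers who were not observed and gives them values with no spread of their own, so the error variance is understated.

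At stake are false positives on any of four outcomes. The SAP also plans no formal adjustment across the four outcomes when their results fit together, so that pattern would be judged on the p-values this rule produces. Where loss depends on the scores, the two sets can be biased differently or in the same direction, so agreement between them is not proof of soundness.

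**Working it through.** **Inputs from the documents.** 60 caregivers per arm (Protocol, Randomization); three visits; the SAP's power statement, "correlation between repeated measures r = .5, alpha = .05"; item counts as above.

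**Assumed.** All missing rates; equal correlation between visits; loss at random and monotone unless stated; a medium effect as f = 0.25.

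**1. The plan's own figure.** Interaction power uses λ = f²·N·m/(1 − r) = 0.0625 × 120 × 3 / 0.5 = 45 on 2 and 236 df. Power is above .999, consistent with the stated .99, so the set-up matches the planned test.

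**2. Why filling inflates.** Fill a fraction d of one visit with that arm's mean at that visit. The true squared standard error of the arm mean is σ²/[n(1 − d)]; the analysis uses about (1 − d)σ²/n. The standard error is therefore too small by the factor 1 − d. A between-arm t-test at that visit has type I error 2[1 − Φ(1.96(1 − d))] = .078, .117 and .170 at d = 10, 20 and 30%. Simulation gave .076, .120 and .172.

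**3. Interaction test, whole surveys filled by arm and visit (simulated, range over runs).**

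| Loss at 3/6 months | Type I error, filled scores | Filled scores alone significant, no effect |
|---|---|---|
| 5/10% | .064–.071 | about .025 |
| 10/20% | .085–.093 | about .05 |
| 20/30% | .129–.134 | about .09 |

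With loss at 6 months only: .054–.059 at 5%, .061 at 10%, .075–.078 at 20%. Complete responses gave .047–.054 in the larger runs (one 4,000-trial run scattered from .043 to .060).

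**4. Interaction test, scattered items filled by arm and visit**, at 2, 5 and 10% of items blank:
- 12 items: .054–.062, .067–.074, .083–.089
- 20 items: .056, .071, .089
- 5 items: .058, .066, .085

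Prorating from the caregiver's own answers gave .049–.052. What drives the excess is the amount missing and the visit-specific mean, not whether a survey or an item is filled.

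**5. Mean pooled over visits.** The interaction test stays at .046–.054. Take an equal effect δ at 3 and 6 months with 10/20% loss. The pooled arm means then differ by δ(0.9 + 0.8)/2.7 = 0.63δ, so the 6-month difference becomes 0.8δ + 0.2 × 0.63δ = 0.926δ, about 7% diluted. A between-arm t-test at 6 months is still inflated: .068, .094 and .118 at 10, 20 and 30% loss. The SAP's follow-up tests come after a significant interaction and are called paired, so these figures apply only if such a between-arm comparison is made.

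**6. Disagreement.** With a true 0.35 SD effect at 3 and 6 months and 10/20% loss, exactly one of the two analyses is significant in about .19 of trials.

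**7. What complete responses discard.** With 2% of items blank independently and all three visits required, retention is .98^36 = 48% (29 per arm) on 12 items, .98^60 = 30% (18) on 20 items and .98^15 = 74% (44) on 5 items. Read per visit, it is .98^12 = 78%, .98^20 = 67% and .98^5 = 90%. Clustered gaps cost fewer.

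**8. Loss that depends on scores.** One arm loses 20% at 6 months, high scorers more often (logistic slope 1 per SD), with no true effect. Filling is by arm and visit. Entries are filled / complete / mixed model.

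| Loss depends on | Bias in 6-month change (SD) | Interaction rejection rate |
|---|---|---|
| Baseline | −0.09 / +0.09 / 0.00 | .105 / .070 / .049 |
| 3-month score | −0.09 / 0.00 / 0.00 | .104 / .068 / .052 |
| Unseen 6-month score | −0.17 / −0.09 / −0.12 | .180 / .067 / .079 |

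In the second row, complete responses are unbiased only at 6 months. The retained caregivers' 3-month mean shifts by about −0.17 SD and, at r = .5, their baseline by half that, so 3-month change is off by −0.17 + 0.085, about −0.09 SD.

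**The case against.** The literal words favour the sponsor. The filling rule names an item; *by group* does not mention visit; and the SAP's design text uses groups for the two arms. If the arm mean is pooled over visits, the interaction test is not inflated. The largest figures need an assumed 20/30% loss, whereas losing 5–10% at 6 months only gives .054–.061. The Protocol (Contact initiated by study staff) pays caregivers for each completed questionnaire, which should limit loss. The SAP also calls this a sensitivity approach and promises disclosure, so a positive result from filled scores alone would be visible.

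Much of this stands: the size is conditional, and disclosure gives partial protection. But the item reading is no escape when the mean is visit-specific (step 4), pooling exchanges inflation for dilution (step 5), and disclosure does not say what is concluded.

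A reader might infer that the sponsor may claim success on whichever result is significant, which would give .074, .097 and .138 at 5/10, 10/20 and 15/30% loss. The SAP does not say that; it promises to report differences.

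A reader might also infer that only a mixed model will do. It will not cure everything: if loss depends on the unseen 6-month score, it is more biased on change than complete responses are (−0.12 against −0.09 SD). Nor is such a model clearly planned already. The SAP does use the term mixed model for its ANOVA, but its analysis text points to classical repeated measures ANOVA, and its missing-data text offers only filling or complete responses.

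**Conclusion.** The point holds and should be fixed. Two things follow from the text alone: no result is decisive, and filled values are analysed as observed. The inflation of the interaction test holds only if the mean is taken by arm and visit. Its size then depends on the amount missing: about .065 to .13 over the whole-survey losses examined, and about .05 to .09 over 2–10% of items blank. Under pooling, the harm is dilution and a possible inflated 6-month between-arm comparison.

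A reader might infer that the planned tests will run at 9 or 13% error. The documents do not support that, because they give no missing rate and do not define the group. Complete responses hold .05 under random loss, but they can discard observed scores and are biased at one or both follow-up visits when one arm's loss depends on scores. The bias figures rest on one-arm loss, slope 1 per SD and r = .5.

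**What to change.** 1. Delete group-mean replacement.
2. Name one main analysis for each outcome. The preferred choice is a likelihood-based mixed model for repeated measures with condition, visit, condition-by-visit and unstructured covariance. It should use every available assessment from all randomised caregivers and supply the follow-up contrasts.
3. For a few blank items, prorate from the caregiver's own answers under a limit the sponsor fixes before analysis; beyond it, treat the scale as missing at that visit.
4. Keep complete cases as a sensitivity analysis, state that it does not replace the main result, and report loss by arm and visit.
5. Optionally, add a sensitivity analysis for loss that depends on unseen scores, since the mixed model is itself biased there.

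The minimum change is to name complete responses as the main analysis, define whether that means per visit or all visits, and drop the filled scores.

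The cost is SAP wording and standard software, with no new data. At 10/20% random loss and a true 0.35 SD effect, apparent power falls from about .53 with filled scores (part of which is the inflated error rate) to about .44 with the mixed model, against about .40 with complete responses.

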Once consent procedures are complete, caregivers receive a Qualtrics link with their initial questionnaire. Identical Qualtrics questionnaires will be sent via email to caregivers in both research conditions at baseline, 3 months, and 6 months. The three sets of questionnaires will be identical, except the baseline questionnaire will also include a contact information form and "Information about person receiving care."

Randomization:

Sixty caregivers will be randomly assigned to the "active in-home technology" condition of the system and the remaining 60 caregivers will be assigned to the "control" condition. Randomization of participants in each group will be determined by People Power employees after the consent process.

Outcome Measures:

All caregivers-regardless of randomized study condition-complete questionnaires on three separate occasions during this study: baseline, 3-months, 6-months. The four outcome measures are: (a) Zarit Burden Interview-Short Form, a questionnaire measuring caregiver burden (Zarit, Reever, & Bach-Peterson, 1980). 12 items are rated on 0-4 scale. Range: 0-48. No subscales. Higher scores represent worse outcomes; (b) Center for Epidemiological Studies Depression Scale (CES-D), a questionnaire measuring depression (Radloff, 1977). 20 items are rated on a 0-3 scale and summed (range = 0-60). There are no subscales. Higher scores represent worse outcomes. The clinical cut-off is usually set at a score of 16; (c) Beck Anxiety Inventory (BAI), a questionnaire measuring anxiety (Beck, Epstein, Brown, & Steer, 1988). 20 items are rated on a 0-3 scale and summed (range= 0-60). Higher scores indicate worse outcomes. There are no subscales. A score greater than 36 is considered to be clinically significant; and (d) Satisfaction with Life Scale, a questionnaire measuring overall life satisfaction and well-being (Diener, Emmons, Larsen, & Griffin, 1985). 5 items scored on a 1-7 scale and summed (Range = 5-35). Lower scores indicate worse outcomes. A score of 20 is considered neutral with higher scores considered increasingly more satisfied and lower scores considered increasingly more dissatisfied.

Contact initiated by study staff

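### The complete-only scoring version tolerates no skipped item, so at skip rates of about 0.5% or more it could lose much of the sample and make the planned two-version comparison hard to read

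*SAP*

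**What the plan says.** For caregivers who do not complete surveys, the SAP (Statistical Methods, Missing Data) states: "we will use a sensitivity analysis approach in dealing with these missing data by performing analysis with 2 versions of scores". The first version is "1) with missing item interpolated using mean replacement by group"; the second is "2) only using responses with 0% missing data". The only follow-up is this: "If the results differ for the two approaches, then we will report on the differences".

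The paragraph does not say whether a response means one scale at one visit, a whole questionnaire, or all of a caregiver's data. It names neither version as primary, does not define a difference, and gives no expected rate of missing items.

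The SAP's Primary Outcomes section lists four scales: the Zarit short form ("12 items are rated on 0-4 scale"), the CES-D and BAI with 20 items each, and the Satisfaction with Life Scale (SWLS) with 5. Each is collected three times. Treatment is tested by the Condition x Time interaction in a repeated measures ANOVA. The Protocol's Randomization section puts 60 caregivers in each arm. Surveys are sent through Qualtrics, and neither document says whether an answer to every item is forced.

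**The concern.** Read literally, one blank item removes an otherwise complete response from version 2. A conventional repeated measures ANOVA then drops that caregiver at all three visits. Version 1 keeps the caregiver, but the value it puts in the blank comes from the group. So neither version fills the blank from the other items that the caregiver answered on the same scale at that visit, which are the closest information available.

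What is at stake is how the comparison of the two versions will be read. If version 2 runs on a much smaller sample, it may lose significance for that reason alone, and the SAP's wording would have this reported as a difference between missing-data approaches. If caregivers in more distress skip more items, the complete-only set is also selected on severity.

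This point covers skipped items in returned surveys. How wholly unreturned surveys are filled under version 1 is a separate matter.

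**Working it through.** **Inputs.** From the documents: 120 caregivers, three visits, scales of 5, 12, 20 and 20 items, r = .5, alpha = .05, and interaction power of .99 for a medium effect. Assumed: an item-skip rate q, independent across items and visits; no dropout; f = 0.25 as the meaning of medium for the interaction.

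**The plan's own figure.** The noncentrality is f² x N x m / (1 - r) = 0.0625 x 120 x 3 / 0.5 = 45, with 2 and 236 degrees of freedom. Power is 0.99999, consistent with the stated .99. The SAP gives no figure on missing data to reproduce.

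**Retention.** Expected caregivers complete at all three visits = 120 x (1 - q)^(3 x items). For a 20-item scale at q = 1% this is 120 x 0.99^60 = 66.

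| q | 5 items | 12 items | 20 items | all 57 items |
|---|---|---|---|---|
| 0.1% | 118 | 116 | 113 | 101 |
| 0.5% | 111 | 100 | 89 | 51 |
| 1% | 103 | 84 | 66 | 22 |
| 2% | 89 | 58 | 36 | 4 |

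The last column applies only if a response means the whole questionnaire and all 57 x 3 = 171 answers must be present.

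**Disagreement at f = 0.25, 20-item scale.** The same formula gives power 0.9997 / 0.996 / 0.906 with 89 / 66 / 36 caregivers. Against 0.99999 with all 120, the gap is about 0.0003 / 0.004 / 0.094. Disagreement on significance is therefore rare up to 1% skipping and about 9% at 2%.

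**How large f = 0.25 is.** If the arms diverge linearly by D standard deviations (SD) over 6 months, the interaction effects are ±D/4 at the first and last visits and 0 at the middle one. So f² = (2/3)(D/4)² = D²/24, and f = 0.25 means D = 0.25 x √24 = 1.22 SD. This is much larger than d = 0.5, the usual reading of the SAP's medium Group difference, so smaller effects also need examining.

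**Disagreement with a modest effect.** The SAP's two versions were simulated at item level on the Condition x Time test with random skipping. With a 0.5 SD latent linear effect they disagreed on p < .05 in about 10 / 22 / 30 / 39% of trials at q = 0.1 / 0.5 / 1 / 2%. A separate simulation (1,500 trials per cell, 20 items, full-data power about .5) gave 8 / 21 / 32 / 43%.

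**Where the disagreement comes from.** In the separate simulation at q = 1%, version 1 rejected in .511 of trials and version 2 in .267, with .319 discordant. If a is the share significant only in version 1 and b the share significant only in version 2, then a + b = .319 and a - b = .244, so a = .28 and b = .04. At 2%, a + b = .430 and a - b = .534 - .171 = .363, so a = .40 and b = .03. Most of the disagreement is version 2 missing an effect that version 1 detects.

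**Disagreement with no effect.** The separate simulation gave 1-2 / 3-5 / 3-6 / 4-8% at the same four skip rates. The 0.5 SD simulation's no-effect counterpart gave about 6-8% at 1%.

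**Skipping that rises with distress.** In a single-visit simulation of a 20-item scale, with an assumed log-rate slope of .7 per SD, the full-data arm difference was -3.61. Complete-only gave -3.03 at 1% (1 - 3.03/3.61 = 16% smaller) and -2.63 at 2% (27% smaller). Own-item-mean scoring gave -3.61 in both. On the SAP's Condition x Time test the complete-only shrinkage was about 15-23% at 1-2%, and own-item-mean scoring matched full data.

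**The case against.** The strongest reply is that every size above rests on a skip rate that the documents do not give. Collection is online, forced answers are possible though not stated, and caregivers are paid \$25 for each questionnaire they complete. The rate could be close to zero, and at 0.1% a 20-item scale loses only about 7 of 120 caregivers. Skips concentrated in a few people would also cost fewer caregivers than the independence formula implies. All of this stands, and it makes the size conditional. It does not supply the missing tolerance.

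The second reply is that version 2 is one half of a declared sensitivity analysis, and version 1 keeps every caregiver with a skipped item. That also stands. A reader might infer that the strict rule biases the trial's result. The documents do not support this, since both versions are run and differences are reported.

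The third reply is that replacing version 2 altogether would leave no analysis free of item imputation, which is the contrast that the two-version design supplies. This is right, and the 0%-missing analysis should be kept. The distress-related shrinkage depends on an assumed slope and shows only what could happen.

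**Conclusion.** The concern holds in a conditional form. Version 2 has no tolerance for a skipped item, and neither version fills a blank from the caregiver's own answers on the scale. At assumed independent skip rates of 0.5-2%, a 20-item scale would keep between about 89 and 36 of 120 caregivers. With an effect near 0.5 SD, the two versions could then disagree on significance in roughly 20-40% of trials.

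A reader might go further and infer that the versions will often disagree by chance. The documents do not support that. They give no skip rate, most of the disagreement is loss of power, and on a single scale it stays under about 10% when there is no effect or when f = 0.25. Disagreement at f = 0.25 would be larger only if completeness were required over the whole questionnaire: 22 caregivers at 1% skipping leave power of 0.697. The SAP does not say which unit it means.

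The figures assume random, independent skipping, no dropout, and an ANOVA that drops a caregiver with any missing visit score. This is worth correcting before analysis, but it does not by itself invalidate the planned result.

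**What to change.** Define completeness per scale and visit. As the main scoring version, score a scale when at least 80% of its items are answered: 10 of 12 on the Zarit short form, 16 of 20 on the CES-D and BAI, 4 of 5 on the SWLS. Fill a skipped item with that caregiver's own mean on the other items of the scale at that visit. Below the threshold, treat that scale score as missing.

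Keep the 0%-missing analysis as supportive only. Report its sample size, estimate and confidence interval beside the main result, so that a loss of significance from a smaller sample is not read as sensitivity to missing data.

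The cost is a few lines of SAP text and scoring code. The downsides are small: own-mean scoring assumes that skipped items resemble the caregiver's other answers, and the 80% cut-off is a convention that does not come from the documents.
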